1.2 STUDY OBJECTIVES

The objectives of the study are:

Primary Objective

• The primary objective of this study is to characterise the PK profile of ivermectin following daily repeated doses for 28 days.

Secondary Objective

• The secondary objective of this study is to characterise the safety and tolerability profile of daily repeated dosing of ivermectin for 28 days.

Exploratory Objective

 The exploratory objective of this study is to evaluate the potential of ivermectin as a prophylactic measure to Severe Acute Respiratory Syndrome Coronavirus 2 (SARS-CoV-2) infection.

1.3 STUDY ENDPOINTS

1.3.1 Primary Endpoint

The primary endpoints of the study are plasma PK concentrations including, but not limited to: maximum plasma concentration (C_{max}), time to reach C_{max} (t_{max}),

area under the plasma concentration-time curve from zero to 24 hours (AUC_{0-24h}),

[figure not shown]
apparent terminal half-life $(t_{1/2})$.

1.3.2. Secondary Endpoint(s)

The secondary endpoint of the study is the clinical safety data from adverse event (AE) reporting, 12-lead electrocardiogram (ECG), vital signs, clinical laboratory evaluations, and physical and neurological examinations in healthy male subjects.

1.3.3. Exploratory Endpoints

The exploratory endpoint of the study is the occurrence of SARS-CoV-2 infection as confirmed by reverse transcription polymerase chain reaction (RT-PCR) test and/or serology.

1.4 STUDY DESIGN

This is a Phase I, double-blind, placebo-controlled, randomised study to determine the PK profile, safety and tolerability of multiple oral doses of ivermectin in healthy male subjects

Up to 24 subjects are planned to be enrolled into 3 cohorts comprising 8 subjects each. In each cohort, 6 subjects will be randomised to receive ivermectin and 2 subjects will be randomised to receive placebo. Multiple-dose oral administration of once daily ivermectin or placebo will occur for 28 days. All cohorts will consist of 2 sentinel subjects, of whom 1 subject will receive ivermectin and 1 subject will receive matched placebo. The remaining subjects in each cohort (6 subjects; 5 subjects ivermectin and 1 subject placebo) will commence treatment after satisfactory review of the safety data up to a minimum of 4 hours postdose on Day 7 from the sentinel subjects, if deemed safe to do so by the Principal Investigator.

The planned dose levels are presented in Table 1.

Table 1: Planned Dose Levels

Cohort 1	Loading dose of 200 μg/kg on Day 1, then 50 μg/kg/day from Day 2 to Day 28
Cohort 2	Loading dose of 200 μg/kg on Day 1, then 75 μg/kg/day from Day 2 to Day 28
Cohort 3	Loading dose of 200 μg/kg on Day 1, then 100 μg/kg/day from Day 2 to Day 28

The dose levels will be administered in an ascending order; progression to the next dose level, and dose selection, will be based on the safety, tolerability and available PK data from the preceding dose cohort(s) (safety, tolerability and PK data [up to Day 14] from a minimum of 4 ivermectin and 1 placebo subjects in the preceding dose cohort). Except for the starting dose, the doses outlined in the Protocol are preliminary, with actual subsequent doses determined based on an ongoing evaluation of the safety, tolerability, and PK data by the Safety Review Committee (SRC; described in Section 4.7).

2 ANALYSIS SETS

2.1 PER PROTOCOL ANALYSIS SET

The Per-Protocol Set will include all randomised subjects that have completed the 28-day dosing period of the trial without major protocol deviations. Subjects withdrawn due to non-compliance (see Section 6.4 of study protocol) will not be included in the Per-Protocol Set. Subjects will be classified according to study drug(s) they actually received.

2.2 SAFETY ANALYSIS SET

The Safety Analysis Set will consist of all subjects who received at least 1 dose of study drug(s). Subjects in the Safety Analysis Set will be classified according to study drug(s) they actually received. Safety data will not be formally tested but will be summarised using descriptive statistics.

2.3 PHARMACOKINETIC ANALYSIS SET

All subjects who receive at least 1 dose of investigational medicinal product (IMP) per the Protocol for whom any postdose data are available and who do not violate or deviate from the protocol in ways that would significantly affect the PK analyses will be included in the PK Analysis Set. The population will be defined by the Study Physician, Pharmacokineticist and Statistician prior to any analyses being performed.

2.4 PROTOCOL DEVIATIONS

Protocol deviations will be categorised as minor/major and deviation category in a blinded manner prior to the database lock for each study part. The sponsor will review protocol deviations throughout the course of the study. All deviations will be listed.

3 DERIVED VARIABLES

3.1 EXPLORATORY ENDPOINT - OCCURRENCE OF SARS-COV-2 INFECTION

Occurrence of SARS-CoV-2 infection will be defined as either a positive PCR or positive serology test result at any point after first dose of the IMP.

[figure not shown]
4 ANALYSIS METHODS

4.1 GENERAL PRINCIPLES

All summary tables, figures and data listings will be produced using SAS software 9.4 or above.

Summaries will be performed by treatment group and overall.

Descriptive statistics will be used for all variables, as appropriate. Continuous variables will be summarised by the number of observations, mean, standard deviation, median, minimum, and maximum. For log-transformed data, the geometric mean, coefficient of variation (CV), median, minimum and maximum will be presented.

Categorical variables will be summarised by frequency counts and percentages for each category.

For AE summaries, the n and % of subjects with event, as well as the number of events, will be shown.

For all endpoints the last observation before the first dose of study treatment will be considered the baseline measurement unless otherwise specified. However, if an evaluable assessment is only available after randomisation but before the first dose of randomised treatment then this assessment will be used as baseline.

Assessments on the day of the first dose where neither time nor a nominal predose indicator are captured will be considered prior to the first dose if such procedures are required by the protocol to be conducted before the first dose.

In all summaries change from baseline variables will be calculated as the post-treatment value minus the value at baseline. The percentage change from baseline will be calculated as:

(post-baseline value - baseline value) / baseline value x 100.

All listings will be ordered by treatment group (ivermectin or placebo), cohort and subject number and will include all available data including unscheduled data.

Unscheduled values will be mapped to the closest prior nominal visit/timepoint. If multiple values exist for a nominal visit/timepoint then the worst value of available results will be used in the summary.

Listings will show the original visit and timepoint as collected on the electronic case report form (eCRF) as well as the mapped visit and timepoint for unscheduled values. An indicator will be included in the listings to indicate which value is utilised in the analysis.

4.2 SUBJECT ACCOUNTABILITY

Summaries of analysis populations and subject disposition will be summarised and listed using all subjects who have signed informed consent. The data summaries will contain the following information:

- Number of subjects randomised
- Number and percent of subjects who received ivermectin/placebo
- Number and percent of subjects who completed the study
- Number and percent of subjects who discontinued early from the study and reason for early discontinuation
- Number and percent of subjects in each of the analysis populations

4.3 DEMOGRAPHICS AND BASELINE CHARACTERISTICS

All randomized subjects will be used for all demographic and baseline characteristics summaries. All demographics and baseline characteristics data will be included in listings. The actual treatment (ivermectin / placebo) received will be utilised in these analyses.

4.3.1 Demographics

Demographics including age, ethnicity, height, weight, gender, body mass index (BMI) will be summarised appropriately. In general, for the continuous demographic variables (i.e., age, height, weight and BMI) results for each treatment group will be summarised using mean, standard deviation (SD), median, and minimum and maximum values. For categorical (nominal) variables (i.e., race, ethnicity, and gender), the number and percentage of subjects will be used.

4.3.2 Medical History

Medical history will be summarised by treatment group using number of observations and percentages of subjects reporting each category. Medical history will be coded into the most recent version of the Medical Dictionary for Regulatory Activities (MedDRA) available when coding activities commence.

4.3.3 Eligibility Laboratory Assessments

Pregnancy test, follicle stimulating hormone test, urine cotinine, urine drugs of abuse, alcohol breath screen, SARS-CoV-2 test and serology will be listed by subject, treatment, and timepoint, as appropriate.

4.4 PRIOR/CONCOMITANT MEDICATIONS AND RESCUE MEDICATIONS

All prior or concomitant and rescue medication data will be included in listings.

Medications will be reported using the most recent version of the World Health Organization drug (WHODRUG) codes available when coding activities commence. Medications will be classified according to the World Health Organization Drug Dictionary (WHODD Version March 2019 or later) ATC code levels 2 to 4.

Prior medications are defined as medications taken prior to the dosing of ivermectin/placebo.

Concomitant medications are defined as medications taken on or after the date/time of ivermectin/placebo regardless of the start date/time. Medications can be classified as both prior and concomitant. Prior and concomitant medications will also be listed by ATC code level 4. Actual treatment received will be utilised in summaries.

4.6 SAFETY PARAMETERS

The objective of the evaluation of the safety variables is to investigate the data for any effects on clinical tolerability and laboratory safety variables.

Safety assessments include AE monitoring, standard laboratory safety evaluations (haematology, blood chemistry, coagulation and urinalysis), supine vital signs (RR, BP, HR and oral temperature), orthostatic vital signs, physical examinations, neurological examinations, and 12-lead ECG.

The analysis of safety will be descriptively summarised by timepoint, as appropriate. Data will be presented by actual treatment received for the purposes of summarising the safety results.

No formal hypothesis testing will be carried out.

4.6.1 Adverse Events

Adverse events will be listed in the following categories:

 Treatment-emergent adverse events (TEAEs) are any AEs with a start date and time on or after dosing with ivermectin/placebo. All TEAEs will be listed and summarised as indicated below

The overall incidence of TEAEs (number and percentage of subjects) as well as the number of events will be summarised by treatment, cohort and overall, categories of degree of severity, serious adverse events (SAEs), causally related TEAEs and SAEs, TEAEs leading to discontinuation of treatment and AEs or SAEs leading to withdrawal.

TEAEs will be summarised at both the subject [number (%) of subjects] and event [number of events] level for the following:

- System Organ Class (SOC) and PT
- SOC and PT and maximum reported severity
- SOC and PT and causal relationship to study drug

These analyses will be repeated for SAEs and treatment related AE if deemed necessary, otherwise only the SAEs by SOC and PT will be performed.

For the incidence at the subject level by SOC and PT; if a subject experiences more than one event within the same SOC and PT, only one occurrence will be included in the incidence.

For the incidence at the subject level by SOC, PT and severity; if a subject experiences more than one event within the same SOC and PT, only the most severe occurrence will be included in the incidence.

4.6.2 Clinical Laboratory Evaluations

Clinical laboratory evaluation results (chemistry, haematology, and coagulation) will be listed for individual subjects and compared to laboratory reference ranges and those values outside of the applicable range will be flagged as high (H) or low (L) and categorised by clinical significance (clinically significant/non-clinically significant). This classification of high, low and normal will be summarised by panel (i.e., chemistry, haematology, and coagulation), laboratory test, visit and timepoint.

For all laboratory variables, baseline value will be calculated as last laboratory value prior to dosing. Change from baseline values at each assessment will be calculated as the assessment value minus the baseline value. The quantitative laboratory data, along with changes from baseline will be summarised using descriptive statistics by timepoint, cohort and treatment.

Urinalysis data will be listed only.

4.6.3 Vital Signs

Vital signs data and oral temperature will be listed for individual subjects.

Vital signs include heart rate (HR), supine and standing systolic blood pressure (SBP), diastolic blood pressure (DBP), respiration rate and body temperature.

Vital signs data along with changes from baseline will be summarised using descriptive statistics by position and timepoint. For each vital sign variable, baseline value will be calculated from the mean of the available triplicate (if collected) predose values.

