1.4.2. Clinical Experience from the Treatment of Onchocerciasis

In clinical trials¹⁹ involving 963 adult patients treated with 100 to 200 μ g /kg ivermectin, worsening of the following Mazzotti reactions during the first 4 days post-treatment were reported: arthralgia/synovitis (9.3%), axillary lymph node enlargement and tenderness (11.0% and 4.4%, respectively), cervical lymph node enlargement and tenderness (5.3% and 1.2%, respectively), inguinal lymph node enlargement and tenderness (12.6% and 13.9%, respectively), other lymph node enlargement and tenderness (3.0% and 1.9%, respectively), pruritus (27.5%), skin involvement including oedema, papular and pustular or frank urticarial rash (22.7%), and fever (22.6%).

Ophthalmological conditions were examined before treatment, at Day 3, and months 3 and 6 after treatment with 100 to 200 μ g /kg ivermectin. Changes observed were primarily deterioration from baseline 3 days post-treatment. Most changes either returned to baseline condition or improved over baseline severity at the month 3 and 6 visits. The percentages of patients with worsening of the following conditions at Day 3, month 3 and 6, respectively, were: limbitis: 5.5%, 4.8%, and 3.5% and punctate opacity: 1.8%, 1.8%, and 1.4%. The corresponding percentages for patients treated with placebo were: limbitis: 6.2%, 9.9%, and 9.4% and punctate opacity: 2.0%, 6.4%, and 7.2%.

The following clinical adverse reactions were reported as possibly, probably, or definitely related to the drug in $\geq 1\%$ of the patients: facial oedema (1.2%), peripheral oedema (3.2%), orthostatic hypotension (1.1%), and tachycardia (3.5%). Drug-related headache and myalgia occurred in $< 1\%$ of patients (0.2% and 0.4%, respectively). However, these were the most common adverse experiences reported overall during these trials regardless of causality (22.3% and 19.7%, respectively).

A similar safety profile was observed in an open study in paediatric patients ages 6 to 13.

The following ophthalmological side effects do occur due to the disease itself but have also been reported after treatment with ivermectin: abnormal sensation in the eyes, eyelid oedema, anterior uveitis, conjunctivitis, limbitis, keratitis, and chorioretinitis or choroiditis. These have rarely been severe or associated with loss of vision and have generally resolved without corticosteroid treatment.

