1.4.3. Post-Marketing Experience

Hypotension (mainly orthostatic hypotension), worsening of bronchial asthma, toxic epidermal necrolysis, Stevens-Johnson syndrome, seizures, hepatitis, elevation of liver enzymes, and elevation of bilirubin have been reported.¹⁹ Conjunctival haemorrhage has been reported in the treatment of Onchocerciasis.

Further details regarding the clinical data can be found in the IB or the Summary of Product Characteristics.¹⁹

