1.5. Risk/Benefit Assessment

Further information about the known and expected benefits and risks and reasonably expected AEs of ivermectin may be found in the current IB and the Summary of Product Characteristics.¹⁹

Details of these risks and the proposed strategy to mitigate/monitor these risks are detailed in [Table 1](#).

In this study, safety will be monitored closely both by subjective reporting and by objective means i.e., serial assessments of vital signs, clinical laboratory evaluations data, physical examinations, 12-lead electrocardiogram (ECG) and comprehensive neurological examinations. This study will be run in a Clinical Research Unit (CRU) with immediate access to hospital facilities for the treatment of medical emergencies. Subjects will remain monitored in the clinic for the first 7 days of dosing and will only be discharged from the CRU at the end of Day 7 if the Investigator deems it safe to do so.

Table 1: Risk/Benefit Assessment

Potential Risk of Clinical Significance	Summary of Data/Rationale for Risk	Mitigation Strategy
Skin rashes and pruritus	SmPC	Physical examinations will be performed regularly throughout the study to identify any rashes and overall TEAEs will be monitored.
Cardiovascular changes	SmPC	Heart rate and blood pressure will be frequently monitored during the study by supine and standing vital signs.
CNS changes	SmPC	Comprehensive neurological examinations will occur frequently during the study to identify any changes.
Gastrointestinal system effects	SmPC	Clinical monitoring of body weight and standard safety laboratory parameters, as well as overall TEAEs will be monitored. Subjects will be withdrawn if effects are severe.
Respiratory system changes; exacerbation of asthma	SmPC	Asthmatic subjects will be excluded.
Ophthalmologic changes	SmPC; IB	Comprehensive neurological examinations will occur frequently during the study to identify any changes.
Haematological changes	SmPC	Subjects will be closely monitored with frequent blood tests during the study. Haematology parameters will be closely monitored throughout the course of the study as dose escalation proceeds. Escalation to higher doses and exposures will only occur if emerging data indicates this is safe and appropriate. Stopping criteria have been added for clinically significant lab results. If indicated, no further dose escalation will occur.

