7.3. Vital Signs and Oral Temperature

Supine and standing vital signs (2 minutes apart), including heart rate, blood pressure and oral temperature will be collected at the timepoints in the Schedule of Assessments. Pre-dose vital signs should be collected within 30 minutes pre-dose.

For timepoints with multiple assessments:

- collect the ECG first,
- then vital signs,
- then the PK blood draw. The PK sample should be collected at the scheduled time post-dose.

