11.5.1.3. Vital Signs

Vital signs (supine and standing systolic blood pressure, diastolic blood pressure, heart rate and body temperature) will be listed for individual subjects. Summary statistics (n, arithmetic mean, median, minimum, and maximum) will be calculated for each parameter by treatment, time, and cohort.

11.5.1.4. 12-Lead Electrocardiogram

Standard 12-lead ECG parameters (RR, PR, QRS, QT, QTcB, QTcF intervals and heart rate) will be listed for individual subjects. Out-of-range ECG values will be flagged as high (H) or low (L). Summary statistics (n, arithmetic mean, median, minimum, and maximum) will be calculated for each parameter by treatment, time, and cohort. Where multiple values are recorded at a timepoint for a subject, the mean of the values will be used in the summary statistics.

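### SAP 4.6.3 summarises supine and standing vital signs separately and derives no standing-minus-supine change, so the final safety tables cannot show how many subjects had an orthostatic fall

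*SAP*

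**What the plan says.** **The risk.** Protocol 1.4.2 gives orthostatic hypotension as drug-related in 1.1% of 963 patients in the onchocerciasis trials. Section 1.4.3 names it as the main form of hypotension reported after marketing. Against cardiovascular changes, Table 1 in section 1.5 offers one mitigation: "Heart rate and blood pressure will be frequently monitored during the study by supine and standing vital signs".

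**The measurement.** Protocol 7.3: "Supine and standing vital signs (2 minutes apart), including heart rate, blood pressure and oral temperature will be collected". SAP 4.6 lists two separate items among the safety assessments: "supine vital signs (RR, BP, HR and oral temperature), orthostatic vital signs".

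**The analysis.** Protocol 11.5.1.3 lists both positions per subject and adds: "Summary statistics (n, arithmetic mean, median, minimum, and maximum) will be calculated for each parameter by treatment, time, and cohort". SAP 4.6.3 also lists the data per subject, and then: "Vital signs data along with changes from baseline will be summarised using descriptive statistics by position and timepoint". SAP 4.1 supplies the statistics for continuous variables: number of observations, mean, SD, median, minimum and maximum.

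In the visible text, neither document derives a standing-minus-supine difference, defines an orthostatic fall or counts subjects who have one. The table shells (SAP 6) are a separate document and were not available.

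**The concern.** Paired readings 2 minutes apart are informative mainly through the difference within each subject. A summary by position keeps the two marginal distributions and drops the pairing. A reader of the safety tables would then see mean supine and mean standing pressure by timepoint, but not whether a modest mean difference comes from small falls in most subjects or large falls in one or two. With 6 ivermectin subjects per cohort, that is the question a reader would ask about a known reaction.

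The adverse event tables fill only part of the gap. Under Protocol 7.6.1.1 and 7.6.1.3, a fall enters them if it causes a symptom such as dizziness, or if the Investigator judges the reading clinically significant. A symptom-free fall not so judged appears only in the listing. Safety is the secondary endpoint, and the protocol's rationale (3.1) says that safety over 28 consecutive days of dosing has not been studied in humans.

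**Working it through.** The plan gives no figure on this point to reproduce. Sample size is not statistically based (Protocol 11.2), and safety is descriptive (SAP 4.6). The check asks whether the planned tables determine the number of subjects with a fall.

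**Inputs.** From the documents: 6 ivermectin and 2 placebo subjects per cohort, 3 cohorts; SAP 4.1 statistics; summaries by position. Assumed: the blood pressures, SDs and correlations below, and limits of 20 mmHg systolic and 10 mmHg diastolic. The documents give no limit.

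**1. Two cohorts with the same tables.** Systolic pressure is 120 mmHg in both positions for every subject at baseline.

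| Subject | Supine (A and B) | Standing A | Change A | Standing B | Change B |
|---|---|---|---|---|---|
| 1 | 135 | 120 | -15 | 105 | -30 |
| 2 | 135 | 120 | -15 | 105 | -30 |
| 3 | 120 | 105 | -15 | 120 | 0 |
| 4 | 120 | 105 | -15 | 120 | 0 |
| 5 | 120 | 120 | 0 | 120 | 0 |
| 6 | 120 | 120 | 0 | 120 | 0 |

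Planned summaries, identical in A and B:
- Supine: mean 125.0, SD 7.75, median 120, range 120 to 135, mean change from baseline +5.0.
- Standing: mean 115.0, SD 7.75, median 120, range 105 to 120, mean change from baseline -5.0.

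Standing minus supine, which is not planned:
- A: mean -10.0, SD 7.75, largest fall 15. Falls of 20 mmHg or more: 0 of 6.
- B: mean -10.0, SD 15.49, largest fall 30. Falls of 20 mmHg or more: 2 of 6.

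The mean change, 115.0 - 125.0 = -10.0, can be recovered from the planned tables. The SD, the largest fall and the count cannot. The counts of 0 and 2 hold for any limit above 15 and up to 30 mmHg. At a limit of 10 or 15 mmHg they are 4 of 6 in A and 2 of 6 in B. They still differ, but in the other direction.

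**2. All pairings of one set of values.** Take supine values 105, 110, 115, 120, 125, 130 (mean 117.5, SD 9.35) and standing values 100, 105, 110, 115, 120, 125 (mean 112.5, SD 9.35). They can be paired in 6! = 720 ways. The mean change is -5.0 in all of them. Falls of 20 mmHg or more occur in 0 subjects in 162 pairings, 1 in 402, 2 in 150 and 3 in 6. The possible count is 0 to 4 subjects at 15 mmHg and 0 to 2 at 25 mmHg.

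**3. Normal model.** Suppose each position has mean change 0 and SD s, with correlation r between positions. Then

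SD of orthostatic change = s × √(2(1 - r)), and P(fall ≥ 20) = 1 - Φ(20 / that SD).

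With s = 10:
- r = 0: SD 14.14, probability 7.9%.
- r = 0.5: SD 10.0, probability 2.3%.
- r = 0.8: SD 6.32, probability under 0.1%.

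The by-position tables are the same in all three cases because they do not report r. Zero correlation is an extreme for two readings 2 minutes apart on one subject, so 7.9% is an outer bound for s = 10.

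**4. Chance flags if a count is added.** P(at least 1 of 6) = 1 - (1 - p)^6, with r = 0.5, per timepoint:
- Systolic fall of 20 mmHg: SD 8, p = 0.0062, 3.7%; SD 10, p = 0.0228, 12.9%; SD 12, p = 0.0478, 25.5%.
- Diastolic fall of 10 mmHg: SD 5, p = 0.0228, 12.9%; SD 6, p = 0.0478, 25.5%; SD 8, p = 0.1056, 48.8%.

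A combined systolic-or-diastolic flag would fire at least as often as the more frequent of the two. The assessment schedule is not visible, so no rate over all timepoints is given.

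**The case against.** The strongest reply is that this is a small Phase I study with descriptive safety only. Both readings are listed for every subject, and with 8 subjects per cohort a reader can work out each fall by hand. Symptomatic falls are counted as adverse events. SAP 4.6.3 carries out Protocol 11.5.1.3 and adds change from baseline, and the unseen shells may already contain the table. All of that stands. It limits the size of the point but does not remove it: a hand calculation after unblinding, with no limit set in advance, is not a planned summary of a known risk.

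Three stronger readings are tempting, and the documents do not support them:
- **That dose escalation is unprotected.** A symptom-free fall meets none of the specific triggers in Protocol 3.2.2.1 and is left to the closing catch-all criterion, which mentions frequency. A reader might infer that SAP 4.6.3 starves that criterion of data. It does not feed it. Under Protocol 3.2.1 the Safety Review Committee reviews vital signs in an Interim Safety Report, and SAP 4.7 leaves the committee's analysis to its charter. Whether the committee sees an orthostatic change cannot be judged from these documents.
- **That Protocol 11.3 promised this derivation.** That section commits the SAP to detail the analyses the protocol plans. The protocol plans no orthostatic derivation, so no promised algorithm is missing.
- **That the tables cannot tell a cohort with no falls from one with two.** Cohort A has four falls of 15 mmHg. It has none only above that limit.

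**Conclusion.** The point holds as a minor gap in the final descriptive safety analysis. The plan names orthostatic vital signs, takes paired readings and then tabulates them in a form that loses the pairing. From the planned tables the mean orthostatic change is recoverable; its spread, its largest value and the number of subjects with a fall are not. In the illustrations, identical tables fit 0 or 2 of 6 subjects in one construction and 0 to 3 of 6 in the other, at 20 mmHg.

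That the tables leave the count open does not depend on the choice of limit, but the particular counts do. They rest on assumed pressures, and the probabilities rest on an assumed normal model. No flaw in the escalation rule is shown. The improvement is worth making because it uses data already collected and costs little. If the table shells already hold the derivation, a reference to them in SAP 4.6.3 closes the point.

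**What to change.** Add to SAP 4.6.3:

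- Orthostatic change is the standing value minus the supine value at the same timepoint, for systolic pressure, diastolic pressure and heart rate.
- Orthostatic change and its change from baseline will be summarised by cohort, treatment and timepoint, including SD, minimum and maximum.
- The number and percentage of subjects whose fall exceeds a stated limit will be tabulated at baseline and at each post-dose timepoint, with systolic and diastolic falls counted separately. Placebo subjects pooled across cohorts (3 × 2 = 6) will be shown as a comparator.

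The sponsor should set the limits before database lock. The 20 and 10 mmHg used above are placeholders. Protocol 3.2.2.1 and the adverse event grading need no change.

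**Cost.** One derived variable and one table, with no new visits, samples or stopping rule. The price is chance flags: per timepoint, about 13% of cohorts would show at least one systolic flag at SD 10 and correlation 0.5. For diastolic falls the figure is about 13% to 49% at SD 5 to 8. Counts should therefore be read against the baseline and placebo counts. Keeping the two pressures apart stops the noisier one from swamping the other.
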